### **Other Medical Conditions**

36. Renal impairment measured as estimated glomerular filtration rate (eGFR) <30 mL/min/1.73 m^2, calculated by chronic kidney disease-epidemiology as determined by central laboratory during screening; for patients on metformin, eGFR <45 mL/min/1.73m^2 (or lower than the country-specific threshold for using the prescribed dose of metformin per local label)

- 37. Known clinically significant gastric emptying abnormality (for example, severe diabetic gastroparesis or gastric outlet obstruction) or chronically take drugs that directly affect gastrointestinal motility
- 38. History of chronic or acute pancreatitis. A patient with a history of acute pancreatitis caused by gallstones may be included in the study if the patient had a cholecystectomy to resolve the problem
- 39. Uncontrolled hypertension (systolic blood pressure ≥160 mm Hg and/or diastolic blood pressure ≥ 100 mm Hg). For participants with uncontrolled hypertension at the screening visit, antihypertensive medication may be started and blood pressure must meet the protocol criterion for hypertension control by the randomization visit
- 40. Uncontrolled inflammatory bowel disease (IBD) and/or not on stable therapy for the last 3 months or clinically symptomatic IBD with C-reactive protein >4 mg/L.
- 41. Any medical condition that, in the opinion of the investigator, may increase the risk of complications related to a liver biopsy (e.g., a known coagulopathy)
- 42. Any of the following cardiovascular conditions within 6 months prior to screening:
  - a. acute myocardial infarction (MI),
  - b. cerebrovascular accident (stroke),
  - c. unstable angina, or
  - d. hospitalization due to congestive heart failure (CHF)
- 43. New York Heart Association Functional Classification IV CHF
- 44. Have a serum calcitonin of
  - (a)  $\geq$ 20 ng/L at Visit 1 if eGFR is  $\geq$ 60 mL/min/1.73 m^2
  - (b)  $\geq$ 35 ng/L at Visit 1 if eGFR is  $\leq$ 60 mL/min/1.73 m^2
- 45. Have a known self or family history (first-degree relative) of multiple endocrine neoplasia type 2A or type 2B, thyroid C-cell hyperplasia, or medullary thyroid carcinoma (MTC)
- 46. Evidence of untreated hypothyroidism or hyperthyroidism based on clinical and laboratory evaluation. Individuals on a stable dose of thyroid replacement therapy for at least the prior 3 months who are clinically euthyroid and who are anticipated to remain on this dose throughout the trial period may be eligible if they meet the other criteria.
- 47. History of an active or untreated malignancy or are in remission from a clinically significant malignancy (other than basal or squamous cell skin cancer, in situ carcinomas of the cervix, or in situ prostate cancer) for less than 5 years
- 48. Any other condition (for example, hypersensitivity) that is a contraindication to GLP-1 receptor agonist
- 49. A transplanted organ (corneal transplants [keratoplasty] allowed) or awaiting an organ transplant
- 50. Any hematological condition that may interfere with HbA1c measurement (for example, hemolytic anemias, sickle cell disease)

### **Prior/Concomitant Therapy**

- 51. Have used insulin for treatment of diabetes within the prior year. However, short-term use of insulin for acute conditions is allowed (≤14 days) in certain situations, such as during a hospitalization or perioperatively (See Section 6.5.1.2)
- 52. Current or previous (within 3 months of screening) use of GLP-1 receptor agonists or any history of allergies to these medications.
- 53. Use of drugs associated with hepatic steatosis (e.g., amiodarone, methotrexate, tamoxifen) for more than 2 weeks in the 3 months prior to screening. If the use of such drugs is anticipated to be medically necessary within the next year, the patient should also be excluded.
- 54. Current use of medication associated with weight gain, except when on stable dose for at least 3 months prior to screening and remaining on stable dose during the study
- 55. Receiving or having received (within 3 months of screening) chronic (>2 weeks) systemic glucocorticoid therapy (excluding topical, intra-ocular, intranasal, intra-articular, or inhaled preparations) or have evidence of a significant active autoimmune disease (such as systemic lupus erythematosus or rheumatoid arthritis) that has required (within the last month) or is likely to require (in the opinion of the investigator) concurrent treatment with systemic glucocorticoids (excluding topical, intra-ocular, intranasal, intra-articular or inhaled preparations) in the next 12 months
- 56. Use of medications or alternative remedies (within 3 months prior to screening; prescribed or over-the-counter) intended to promote weight loss. These include, but are not limited to: Saxenda [liraglutide 3.0 mg], Alli®/Xenical® [orlistat], Meridia® [sibutramine], Acutrim® [phenylpropanolamine], Sanorex® [mazindol], Apidex® [phentermine], BELVIQ® [lorcaserin], QsymiaTM [phentermine/topiramate combination], Contrave® [naltrexone/bupropion]. (See also Inclusion criteria #9)
- 57. Unwillingness to discontinue over-the-counter (herbal) medication that, in the opinion of the investigator, can interfere with the study
- 58. Active and chronic use of anticoagulants (other than aspirin or nonsteroidal anti-inflammatory drugs [NSAIDs]) that, in the opinion of the investigator, increases the risk of severe bleeding during the liver biopsy.

### **Prior/Concurrent Clinical Study Experience**

- 59. Are currently enrolled in any other clinical study involving an investigational product or any other type of medical research judged not to be scientifically or medically compatible with this study
- 60. Have participated within the last 6 months in a clinical study involving an investigational product

#### **Other Exclusions**

- 61. Investigator site personnel directly affiliated with this study and/or their immediate families. Immediate family is defined as a spouse, parent, child, or sibling, whether biological or legally adopted
- 62. Lilly employees
- 63. Unwilling or unable to comply with study diary or questionnaire completion required to record data from the participant

#### **5.2.1.** Rationale for Select Exclusion Criteria

Marijuana should not be used during the study because there are mixed data on its effect on the liver, particularly in NASH. Use of CBD oil is also discouraged because there are data indicating that it can raise liver enzymes, which could result in unnecessary follow up tests.

# **5.3.** Lifestyle Considerations

Medical staff will provide weight management counseling per the SoA (Section 1.3), which will include recommendations on diet and physical activity according to site programs. Based on the counseling provided by the site personnel, participants should follow a healthy lifestyle plan throughout the course of the study. Diet and physical activity counseling may be reviewed throughout the study as needed. Appendix 6 (Section 10.6) provides suggested diet and physical activity recommendations for sites that do not have programs and that may be modified as appropriate locally.

Patients will report to the clinical research site for safety assessments and will remain in the clinic until all procedures for that visit are complete and the investigator has deemed it safe to release the patient from the clinic. There will be no inpatient stays. In addition, patients will report to the clinical research site for pharmacokinetic (PK)-specific visits.

**Meals/Diet** – Patients will fast for at least 8 hours overnight prior to each outpatient visit where fasting samples are drawn or for at least 8 hours when weight measurements are taken.

**Alcohol** – Alcohol will not be permitted 8 hours prior to the study site visits, until the patient has been discharged from the clinical research site.

**Blood Donation** – Study participants should be instructed not to donate blood or blood products during the study and for 8 weeks following the study.

### 5.4. Screen Failures

Screen failures are defined as participants who consent to participate in the clinical study but are not subsequently randomly assigned to study intervention due to not meeting inclusion and/or exclusion criteria. A minimal set of screen failure information is required to ensure transparent reporting of screen failure participants to meet the Consolidated Standards of Reporting Trials (CONSORT) publishing requirements and to respond to queries from regulatory authorities. Minimal information includes demography, screen failure details, eligibility criteria, and any SAE.

Individuals who do not meet the criteria for participation in this study (screen failures) may be rescreened only once at the discretion of the investigator. Before rescreening is performed, the patient must sign a new ICF and receive a new identification number. If, in the opinion of the investigator, an ineligible lab test result is the result of an error or extenuating circumstance, then that parameter can be retested once without the patient having to be rescreened.

Patients who did not meet eligibility criteria for liver biopsy or the histological inclusion criteria based on liver biopsy results may not be rescreened.

Patients whose screening HbA1c is outside of inclusion/exclusion criteria may be rescreened 3 months after adjustments in allowed glucose-lowering medications are made. While patients on stable doses of DPP-4 inhibitors are eligible for study entry, treatment with DPP-4 inhibitors needs to be discontinued prior to randomization. For patients treated with a DPP-4 inhibitor and whose HbA1c is  $\leq$ 8% at the screening visit, this medication must be discontinued with no repeat screening required; the randomization visit should occur approximately 3 months after the screening visit and discontinuation of the DDP-4 inhibitor so that a new baseline HbA1c may be established at randomization. For patients treated with a DPP-4 inhibitor and whose HbA1c is  $\geq$ 8% but  $\leq$ 9.5% at the screening visit, this medication must be discontinued for eligibility into the study, but a rescreening laboratory collection will be required to ensure that the HbA1c is  $\leq$ 9.5% prior to the liver biopsy (Visit 2).

### 6. Study Intervention

Study intervention is defined as any investigational intervention(s), marketed product(s), placebo, or medical device(s) intended to be administered to a study participant according to the study protocol.

# 6.1. Study Intervention(s) Administered

The following table shows the randomized study interventions for the entire study. All doses will be administered SC QW using a single-dose prefilled syringe.

Treatment Group						Treatm	ent Period Interv	val
	Weeks 0 to 3	Weeks 4 to 7	Weeks 8 to 11	Weeks 12 to 15	Weeks 16 to 19		Weeks 20 to 52	
15 mg tirzepatide	2.5 mg	5 mg	7.5 mg	10 mg	12.5 mg	15 mg		-
10 mg tirzepatide	2.5 mg	5 mg	7.5 mg	10 mg —				-
5 mg tirzepatide	2.5 mg	5 mg —						→
Placebo								→

The sponsor will provide tirzepatide and placebo in prefilled syringes. These will be dispensed via an interactive web-response system (IWRS). Prefilled syringes will be packaged in cartons to be dispensed. Clinical trial materials will be labeled according to the country's regulatory requirements.

The actual time of dose administrations will be transcribed in patient diaries and provided to the sponsor.

The investigator or designee is responsible for the following:

- Explaining the correct use of the investigational agent to the participant
- Verifying that instructions are followed properly
- Maintaining accurate records of investigational product dispensing and collection as well as records of interruptions in study drug administration
- Instructing the participant to discard all used syringes for tirzepatide in a closeable, puncture-resistant container and dispose according to local regulations

#### **6.1.1.** Medical Devices

Tirzepatide and matching placebo will be provided in prefilled syringes.

# 6.2. Preparation/Handling/Storage/Accountability

1. The investigator or designee must confirm appropriate temperature conditions have been maintained during transit for all study intervention received and any discrepancies are

- reported and resolved before use of the study intervention. Refer to the study drug label for specific storage conditions.
- 2. Only participants enrolled in the study may receive study intervention and only authorized site staff may supply or administer study intervention. All study intervention must be stored in a secure, environmentally controlled, and monitored (manual or automated) area in accordance with the labeled storage conditions with access limited to the investigator and authorized site staff.
- 3. The investigator, institution, or the head of the medical institution (where applicable) is responsible for study intervention accountability, reconciliation, and record maintenance (that is: receipt, reconciliation, and final disposition records).

# 6.3. Measures to Minimize Bias: Randomization and Blinding

This is a double-blind study. Patients will be stratified at randomization based on T2DM status (Yes or No) and the region (Japan, US including Mexico, and Europe including Israel). Stratification will ensure the number of patients in each stratum will be balanced across different treatment arms.

To preserve the blinding of the study, a minimum number of Lilly personnel will see the randomization table and treatment assignments before the study is complete.

Emergency unblinding for AEs may be performed through the IWRS, which may supplement or take the place of emergency codes generated by a computer drug-labeling system. This option may be used ONLY if the participant's well-being requires knowledge of the participant's treatment assignment. All calls resulting in an unblinding event are recorded and reported by the IWRS.

If an investigator, site personnel performing assessments, or participant is unblinded, the participant must be discontinued from the study. In cases where there are ethical reasons to have the participant remain in the study, the investigator must obtain specific approval from a Lilly clinical research physician (CRP) or clinical research scientist (CRS) for the participant to continue in the study.

In case of an emergency, the investigator has the sole responsibility for determining if unblinding of a participant's treatment assignment is warranted for medical management of the event. The participant safety must always be the first consideration in making such a determination. If a participant's treatment assignment is unblinded, Lilly must be notified immediately. If the investigator decides that unblinding is warranted, it is the responsibility of the investigator to promptly document the decision and rationale and notify Lilly as soon as possible.

# **6.4.** Study Intervention Compliance

Study drug compliance will be determined by the following:

- Study drug administration data will be recorded by the patient in the patient study diary and reviewed by the investigator at each study visit.
- The patients will be instructed to return any unused study drug and/or empty cartons at the next visit to the study site for the purpose of performing drug accountability.

Treatment compliance for each visit interval is defined as taking at least 75% of the required doses of study drug. Similarly, a patient will be considered significantly noncompliant if he or she is judged by the investigator to have intentionally or repeatedly taken more or less than the prescribed amount of medication.

In addition to the assessment of a patient's compliance with the study drug administration, other aspects of compliance with the study treatments will be assessed at each visit based on the patient's adherence to the visit schedule, completion of study diaries, and any other parameters the investigator considers necessary.

Initially, patients considered to be poorly compliant with their medication and/or the study procedures will receive additional training and instruction, as required, and will be reminded of the importance of complying with the protocol.

# 6.5. Concomitant Therapy

Any medication or vaccine (including over-the-counter or prescription medicines and acetaminophen/paracetamol), vitamins, and/or herbal supplements that the participant is receiving at the time of enrollment or receives during the study must be recorded along with:

- Reason for use
- Dates of administration including start and end dates
- Dosage information including dose and frequency

The Medical Monitor should be contacted if there are any questions regarding concomitant or prior therapy.

Initial doses of tirzepatide delay gastric emptying and have the potential to transiently impact the rate of absorption of concomitantly administered oral medicinal products. Tirzepatide should be used with caution in patients receiving oral medicinal products that require rapid gastrointestinal absorption following the initial doses of tirzepatide as exposure to oral medications may be increased.

### 6.5.1. Hyperglycemia Rescue

Although the use of rescue medications is allowable during the study, the use of rescue medications should be delayed, if possible, for at least 1 month after initiation of study drug. The date and time of rescue medication administration as well as the name and dosage regimen of the rescue medication must be recorded.

### 6.5.1.1. Hyperglycemia Rescue Criteria

Hyperglycemia rescue criteria will be determined from weekly fasting self-monitored blood glucose (SMBG) values recorded in T2DM participant diaries. If an SMBG value equal or greater to the glycemic threshold for rescue (See definitions below) is recorded, that value should be confirmed by repeat fasting SMBG within 48 hours. Intensification of T2DM therapy should be initiated if confirmed fasting glucose values are:

• ≥15.0 mmol/L (270 mg/dL) from baseline to Week 6 over at least a 2-week period (at least 2 consecutive values) post-randomization

- ≥13.3 mmol/L (240 mg/dL) from Week 6 to Week 12 over at least a 2-week period (at least 2 consecutive values)
- ≥11.1 mmol/L (200 mg/dL) from Week 12 to end of trial over at least a 2-week period (at least 2 consecutive values)

In addition, if HbA1c is >9.0% at Week 12 or >8.0% at Week 26 or later in the study, glucose-lowering therapy should be adjusted to improve glycemic control as outlined in Section 6.5.1.2. In the event a participant's HbA1c values are less than these thresholds but are higher than what the investigator feels comfortable leaving untreated, glucose-lowering medication can be adjusted. In addition, if patients develop symptoms of hyperglycemia (e.g. polyuria and polydipsia), the investigator should implement measures to determine glycemic control, and adjust as necessary. For patients newly diagnosed with T2DM during the trial, SMBG and appropriate glucose-lowering therapy should be initiated per protocol (Section 6.5.1.2).

### **6.5.1.2.** Hyperglycemia Rescue Medication

Participants with T2DM who develop persistent severe hyperglycemia during the treatment period may be candidates for glucose-lowering rescue therapy and should be considered for addition of, or dose increases of, glucose-lowering medications.

The study site will supply rescue medication that will be obtained locally. Initiation or dose increase of the following may be used as rescue therapy:

- Metformin
  - Do not initiate or increase the dose of metformin when the eGFR
     <45 mL/min/1.73 m² (or lower than country-specific threshold for using the prescribed dose of metformin per local label)

- Sulfonylureas
- Long-acting basal insulin, when
  - o Participant has persistent severe hyperglycemia, and
  - o Participant is at maximal tolerated doses of metformin and/or sulfonylurea (or has an intolerance or contraindication to these medications)

Dose increases of the following are NOT allowed during the study:

- SGLT-2 inhibitors
- TZDs

Initiation of the following is NOT allowed during the study:

- GLP-1 receptor agonists (See Section 5.2)
- DPP-4 inhibitors (See Section 5.2).
- SGLT-2 inhibitors
- TZDs

While avoiding the classes of glucose-lowering medications not allowed by the protocol, investigators should follow national standards of care for diabetes management in respective

participating countries or the American Diabetes Association/European Association for the Study of Diabetes guidance (Inzucchi et al. 2015).

### 6.5.2. Management of Participants with Gastrointestinal Symptoms

In the Phase 2 program, the most commonly reported treatment-emergent adverse events (TEAEs) for participants receiving tirzepatide were nausea, vomiting, and diarrhea. To mitigate GI symptoms and manage participants with intolerable GI AEs, the investigator should:

- Advise patients to eat smaller meals, for example, splitting 3 daily meals into 4, or more smaller meals, and to stop eating when they feel full. Also, patients may be informed that lower-fat meals could be better tolerated.
- Prescribe symptomatic medication (for example, anti-emetic or antidiarrheal medication) per local country availability and individual patient needs. Use of symptomatic medication should be captured as concomitant medication in the eCRF.
- Temporarily interrupt study drug (omit 1 dose, the patient will take 3 of 4 doses at that dose level). The data related to temporary interruption of study treatment should be documented in source documents and entered on the eCRF.
- After the interruption, restart at the same dose with the patient taking medication to alleviate their GI symptoms.

If intolerable GI symptoms or events persist despite the above measures, see Section 6.6.

### 6.6. Dose Modification

Patients who do not tolerate the first dose escalation, in other words from 2.5 mg to 5 mg (or placebo equivalent), will need to discontinue from study treatment. If a patient does not tolerate a dose level higher than 5 mg for 2 weeks (e.g., moderate-to-severe nausea, vomiting, or diarrhea) and the investigator does not believe that the patient will tolerate the dose with further exposure, then the investigator may reduce the dose to the next lower 5 mg incremental dose (e.g., 5 mg or 10 mg). If this dose is tolerated after 4 weeks, the dose should be increased by 2.5 mg every 4 weeks until the target dose is achieved. If this dose escalation is not tolerated, the dose should be reduced to the next lower 5 mg incremental dose that was tolerated (e.g., 5 mg or 10 mg). The patient will remain at that dose level for the duration of the study. Maintenance doses of 2.5 mg, 7.5 mg, or 12.5 mg will not be allowed.

In order to maintain blinding of the investigator and patient, the investigator should call the IWRS to explain that the patient needs the dose reduced and IWRS will provide dispensing information. Dose reductions may occur at unscheduled visits.

# 6.7. Intervention after the End of the Study

Tirzepatide will not be made available to participants after conclusion of the study.

# 7. Discontinuation of Study Intervention and Participant Discontinuation/Withdrawal

# 7.1. Discontinuation of Study Intervention

Possible reasons leading to permanent discontinuation of investigational product:

- Subject Decision
  - o the participant or the participant's designee (for example, parents or legal guardian) requests to discontinue investigational product.
- Investigator Decision
  - o the investigator decides that the patient should be discontinued from the study medication
- Any medication for weight loss is given for more than 1 week
- Participants will be discontinued from the investigational product in the following circumstances:
  - o Diagnosis of cirrhosis after randomization (refer to Section 8.3.7.1 for details)
  - o Pancreatitis or pancreatic cancer (refer to Section 8.3.7.2 for details)
  - o Diagnosis of MTC after randomization
  - Diagnosis of an active or untreated malignancy (other than basal or squamous cell skin cancer, in situ carcinomas of the cervix, or in situ prostate cancer) after randomization
  - Any severe injection site reaction, or 2 or more moderate injection site reactions occurring a week or more apart
  - o Any significant study drug-related hypersensitivity reaction
  - Any TEAE, SAE, or clinically significant laboratory value for which the investigator believes that permanent study drug discontinuation is the appropriate measure to be taken
  - Any TEAE or SAE considered possibly or probably related to study drug that is severe or medically significant but not immediately life-threatening; or where hospitalization or prolongation of hospitalization is indicated; or is disabling; or limits self-care activities of daily living
  - Any TEAE or SAE regardless of attribution to study drug that has lifethreatening consequences or urgent intervention is indicated
  - o A female participant becomes pregnant
  - o Diagnosis of T1DM or latent autoimmune diabetes in adults
- If the patient develops any exclusion criteria during the course of the study, the investigator should call the sponsor to determine whether discontinuation of study drug is necessary

• Significant non-compliance with the protocol

If study drug is permanently discontinued, the patient should remain in the study if possible. The patient may continue participation in the study, attend all visits, and undergo most protocol procedures.

Participants discontinuing from the investigational product prematurely for any reason should complete AE and other follow-up procedures per Section 1.3 (Schedule of Activities), Section 8.3 (Adverse Events and Serious Adverse Events), and Section 8.2 (Safety Assessments) of the protocol.

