# 7.1.1. Interruption of Study Intervention

After randomization, the investigator may interrupt study drug, for example, due to an AE (e.g., nausea and vomiting), or a clinically significant laboratory value. If study drug interruption is due to an AE, the event is to be followed and documented. Every effort should be made by the investigator to maintain patients in the study and to restart study drug promptly after any interruption, as soon as it is safe to do so (See Section 7.1.2 for restarting study drug). The dates of study drug interruption and restart must be documented. The data related to interruption of study treatment will be documented in source documents and entered on the eCRF. Patient noncompliance should not be recorded as interruption of study drug on the eCRF.

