### 7.1.3. Interruption/Discontinuation due to a Hepatic Event or Liver Test Abnormality

Participants who are interrupted/discontinued from investigational product due to a hepatic event or liver test abnormality should have additional hepatic safety data collected via case report form (CRF).

Interruption/discontinuation of the investigational product for abnormal liver tests should be considered by the investigator when a participant meets one of the following conditions after consultation with the Lilly-designated medical monitor. These criteria differ based on the baseline liver test findings and are summarized below (Regev et al. 2019). If study drug is interrupted, it can be restarted only if another etiology is identified and liver enzymes return to baseline.

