# 8.3.7.7. Thyroid Malignancies and C-Cell Hyperplasia

Individuals with personal or family history of MTC and/or multiple endocrine neoplasia type 2 (MEN-2) will be excluded from the study.

The assessment of thyroid safety during the trial will include reporting of any case of thyroid malignancy including MTC and papillary carcinoma and measurements of calcitonin. This data will be captured in specific eCRFs. The purpose of calcitonin measurements is to assess the potential of tirzepatide to affect thyroid C-cell function, which may indicate development of C-cell hyperplasia and neoplasms.

Study drug should be discontinued (after first confirming the value) if postrandomization serum calcitonin value increases.

- For eGFR  $\geq$ 60 mL/min:  $\geq$ 20 pg/mL and has increased  $\geq$ 50% over the screening value.
- For eGFR <60 mL/min:  $\geq$ 35 pg/mL and has increased  $\geq$ 50% over baseline.

A consultation with a thyroid specialist (if not available, an endocrinologist) should be obtained. If the increased calcitonin value is observed in a patient who has administered a medication that is known to increase serum calcitonin, this medication should be stopped and calcitonin levels should be measured after an appropriate washout period. If the confirmed calcitonin value is <20 pg/mL (eGFR  $\ge$ 60 mL/min) or <35 pg/mL (eGFR <60 mL/min), tirzepatide should be restarted once safe to do so.

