# 8.3.7.10. Hypersensitivity Events

All allergic or hypersensitivity reactions will be reported by the investigator as either AEs or, if any serious criterion is met, as SAEs. Additional data, such as type of reaction and treatment received, will be collected on any AEs or SAEs that the investigator deems related to study drug via the eCRF created for this purpose. Study drug should be temporarily interrupted in any individual suspected of having a severe or serious allergic reaction to study drug. Study drug may be restarted if and when it is safe to do so, in the opinion of the investigator. If study drug is permanently discontinued, the patient should continue in the trial to collect all planned efficacy and safety measurements.

Lab testing should be performed at the time of a systemic hypersensitivity event. The management of the AE may warrant laboratory testing beyond that described below and should be performed as clinically indicated.

In the presence of generalized urticaria or if anaphylaxis is suspected and after the subject has been stabilized, samples described below should be obtained within 1-2 hours of the event; however, samples may be obtained as late as 12 hours after the event as analytes can remain altered for an extended period of time. The time at which the sample was collected should be recorded and a follow-up sample should be obtained at the next regularly scheduled visit or after 4 weeks, whichever is later.

Analytes to be evaluated in the sample:

- Tryptase
- ADA and tirzepatide concentration (PK)
  - o If a drug specific immunoglobulin E (IgE) assay is not available, a commercially available alternative test that can indicate the presence of drug-specific IgE in serum is the basophil activation test (BAT)
- Complement
  - o C3a and C5a
- Cytokines
  - o IL-6, IL-1β, IL-10 (or any cytokine panel that includes these 3 cytokines)

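### Section 6.6 allows dose reduction and re-escalation after severe, drug-related GI events for which Section 7.1 requires study drug to stop

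*Protocol*

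**What the plan says.** Protocol Section 7.1 lists circumstances in which participants are to be taken off study drug. Two matter here: "Any TEAE or SAE considered possibly or probably related to study drug that is severe or medically significant but not immediately life-threatening" and "Any significant study drug-related hypersensitivity reaction". The first entry continues with events that need hospitalization, are disabling or limit self-care. A further entry covers life-threatening events, or events needing urgent intervention, whatever their attribution. None of these exempts GI events.

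Section 6.6 covers intolerance above 5 mg: "If a patient does not tolerate a dose level higher than 5 mg for 2 weeks (e.g., moderate-to-severe nausea, vomiting, or diarrhea". If the investigator does not expect tolerance to develop, the dose may be reduced to 5 mg or 10 mg. If that dose is tolerated after 4 weeks, it is to be raised again by 2.5 mg every 4 weeks towards target. Section 6.5.2 sends persistent intolerable GI events to 6.6, not to 7.1. Section 8.3.7.12 asks only for data collection on severe GI events.

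Three restart provisions lie nearby:
- Section 7.1.1: "Every effort should be made by the investigator to maintain patients in the study and to restart study drug promptly after any interruption", once it is safe. It points only to 7.1.2.
- Section 6.5.2: restart at the same dose after omitting one dose for GI symptoms.
- Section 8.3.7.10: "Study drug should be temporarily interrupted in any individual suspected of having a severe or serious allergic reaction to study drug", followed by "Study drug may be restarted if and when it is safe to do so, in the opinion of the investigator".

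**The concern.** For one class of event, two sections give answers that cannot both be acted on: a permanent stop, or a lower dose followed by re-escalation. The class is foreseeable. Section 6.5.2 names nausea, vomiting and diarrhea as the most commonly reported treatment-emergent events with tirzepatide. Section 4.3 says GI events became more frequent with dose in the Phase 2 diabetes study. Section 8.3.7 lists severe GI events as being of special interest.

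What is at stake is participant safety and uniform conduct. A site working from 6.6 can re-escalate a participant after an event that 7.1 says must end treatment. Two sites can handle the same event differently, each citing the protocol. The sponsor already treats this class as serious at study level: under Section 10.1.7.1, two participants with the same severe, related event trigger a safety investigation.

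**Working it through.** **Text check.** The main question is one of wording, so the sections are compared by type of GI event at a dose above 5 mg.

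| GI event | Section 7.1 | Section 6.6 | Conflict? |
|---|---|---|---|
| Moderate, meets no 7.1 criterion | Silent | May reduce, then re-escalate | No |
| Moderate, but meets another 7.1 criterion (for example, related and needing hospitalization) | Stop | May reduce, then re-escalate | Yes |
| Severe, judged possibly or probably related | Stop | May reduce, then re-escalate | Yes |
| Severe, judged unrelated, not life-threatening and no urgent intervention needed | Silent on these two entries | May reduce, then re-escalate | No |

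Neither section refers to the other on this point. Section 8 bars waivers and sends immediate safety concerns to the sponsor, but it sets no order of precedence.

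**Timing.** In the Section 6.1 dosing table, the first dose above 5 mg is 7.5 mg at Week 8. Adding the 2 weeks of intolerance in 6.6 gives about Week 10. Under Section 8.1.1, a participant who stops before Week 36 has no second biopsy. From Week 10 to Week 35, then, applying 7.1 instead of 6.6 costs the primary-endpoint biopsy. Sites are blinded, so they face this decision in all four arms.

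**Power cost of applying 7.1.** Inputs from Protocol Section 9.2 and SAP Section 2.2: 42.5% versus 12.5% response, two-sided 0.05, 196 randomized equally, 20% dropout. Per arm, 196 / 4 = 49 and 49 × 0.8 = 39.2, which the plan gives as about 40.

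Pooled-variance normal approximation:

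power = Φ[(0.425 − 0.125 − 1.960 × SE0) / SE1]

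SE0 uses the pooled rate (0.275 with equal arms) and SE1 the separate rates.

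- 40 per arm: SE0 = 0.0998, SE1 = 0.0940; (0.300 − 0.1957) / 0.0940 = 1.109; power 86.6%. The plan's claim of at least 80% is reproduced.
- 34 per arm: SE0 = 0.1083, SE1 = 0.1020; (0.300 − 0.2123) / 0.1020 = 0.860; power 80.5%.
- 33 per arm: power 79.3%.

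Fisher's exact test, by full enumeration: 82.1% at 40 per arm, 80.0% at 38, 78.5% at 37.

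The margin for equal additional loss is therefore 40 − 34 = 6 per arm by pooled z, and 40 − 38 = 2 per arm by Fisher's exact. If the loss falls on one active arm only, 28 versus 40 gives 80.3% by pooled z but 76.7% by Fisher's exact.

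**The case against.** **A site can comply with both sections.** 6.6 is permissive and 7.1 mandatory, so a site can decline the reduction and stop the drug. That is true, and it makes the repair small. But 6.6 still names severe events as grounds for reduction, and a site that takes it at its word breaches 7.1.

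**The opening of 7.1 speaks of possible reasons.** It does, but the sub-list holding these criteria is worded as an obligation. Judgement enters in grading severity and relatedness. Once both are met, no discretion is left.

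**A reader might infer that the restart clauses also contradict 7.1.** The documents do not support that. Section 7.1.1 is a subsection of 7.1, concerns interruption, and is limited by safety. Section 6.5.2 does not tell a site to keep on drug a participant who meets a 7.1 criterion. Section 8.3.7.10 speaks of a suspected reaction and goes on to provide for permanent discontinuation. It can be read in sequence with 7.1: interrupt on suspicion, then stop if the reaction proves significant and related. What stands is a missing cross-reference. Other restart rules do state a condition: for hepatic events, "If study drug is interrupted, it can be restarted only if another etiology is identified and liver enzymes return to baseline"; for calcitonin, the clause beginning "If the confirmed calcitonin value is <20 pg/mL".

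**A reader might also infer bias or a power problem in the primary analysis.** That is not supported either. SAP Section 3.2 makes permanent discontinuation an intercurrent event under a hypothetical strategy, and participants on a reduced dose are analysed as randomized. Both routes have a specified analysis, and no event rate is given from which to size an effect.

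**Conclusion.** Section 6.6 is wrong as written, within narrow limits. The conflict covers GI events above 5 mg that are severe and judged possibly or probably related, or that meet another 7.1 criterion. It does not extend to moderate events that meet none. Sections 6.5.2, 7.1.1 and 8.3.7.10 need clarification, not correction.

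The number of participants affected cannot be estimated from the documents. The power margins of about 6 or about 2 per arm assume that the extra stops come on top of the planned 20% dropout and fall equally on both arms. They may instead lie within that 20%, since 7.1 is already mandatory. The SAP's primary test is a logistic regression adjusted for diabetes status and region, which neither calculation models. The margins show scale only; the case for the change is participant safety and consistent conduct.

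**What to change.** In Section 6.6, change the example to *moderate nausea, vomiting, or diarrhea that meets no Section 7.1 criterion*, and add *subject to Section 7.1* to the dose-reduction provision.

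As clarification only, add *subject to Section 7.1* to 6.5.2, to 7.1.1 and to the restart sentence of 8.3.7.10. Do not write into 8.3.7.10 a permission to restart when a reaction is judged not significant or not related. That wording would admit a life-threatening reaction judged unrelated, and a severe related reaction judged not significant (a term that 7.1 leaves undefined). Section 7.1 stops both.

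If the sponsor does intend severe GI events to be managed by dose reduction, it must write that exception into 7.1. The amendment history (Protocol Section 10.11, Amendment b) records that the severity and relatedness criteria were added at regulatory request, so an exception would loosen a rule made for regulators.

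The cost is one changed example, a short cross-reference in four sections, and a note to sites with the next amendment. No visits, procedures or participants are added. The downside is that some participants with severe related GI events will stop instead of continuing at a lower dose.
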